To address the above gaps in knowledge, we designed and are close to finishing an original 2-year, randomized, controlled 1:1 RCT (continue vs discontinue), rater-blinded DMT discontinuation study (DISCOMS, NCT#: 03073603). The last of 260 patients was enrolled on February 4, 2020. Last patient, last visit will be in August 2021 (note, not all will be followed for two years, with shortest final follow-up at 18 months in a minority of late enrollees). While this is the first RCT of DMT discontinuation, others are underway in France (NCT03653273) and The Netherlands (NCT04260711). Among focus groups employed during the operation of DISCOMS, it was very clear that one of the main limitations of the study was relatively short duration of the follow-up. Herein we propose to address this limitation with a non-randomized, yet rater-blinded protocol to extend the follow-up of 100 participants from the original DISCOMS cohort by at least 12 months. In essence, the first 100 participants from the DISCOMS primary study who have already successfully completed the primary DISCOMS study (i.e. did not fail on the primary outcome of a new relapse or Brain MRI lesion), retained their original drug assignment (continue or discontinue) at the end of their participation in DISCOMS, and agree to participate in the extension will be included for a minimum of 12 more months of follow-up as assessed at a single visit. This is a pragmatic clinical trial, based on real world patterns of patient decision-making. As such, study visits will be attached to routine office visits when possible, and the patient/their insurance will be responsible for payment of standard of care aspects related to the study. This will include drug costs, the annual brain MRI scans at year one, and all routine safety monitoring as would be obtained in a typical office setting for that individual medication. The funding agency, EMD Serono (a biopharmaceutical business of Merck Pharmaceuticals KGaA), will be responsible financially for all research aspects, including data acquisition, all research personnel, and all regulatory review. In addition, while this is a discontinuation trial, all patients will be aware of their medication assignment, while observers of the main outcomes (relapses, MRI changes and the EDSS) will be blinded.

III. Research Methods

A. Outcome Measure(s):

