All participants will undergo the T_1 visit, which will include a formal, blinded relapse assessment by the Examining Physician (EDSS rater) in conjunction with the PI (see section E). Prior to enrollment, the enrolling physician will certify, based on their personal review of the prior MRI scans and/or reports which will include data from the 24 month primary DISCOMS trial, that the scans have been stable for a minimum of 4.5 years (review of minimum of two scans, although it could be more, separated by at least 4.5 years). MRI scans at T_1 , 36+ months after onset of participation in the primary trial, will be performed as per usual SOC, paid for by patient insurance, at whatever site is normally used by the patient (preferably the same scanner each time, and preferably the same scanner as the investigation site), and should be done on a MRI machine with magnet 1.5 Tesla or greater, with and without contrast. Gadolinium may be withheld at the discretion of the PI or request of the patient. The window for T_1 MRIs will be 60 day before or 120 days after the T_1 study visit, and will be analyzed by a central, board-certified, blinded neuro-radiologist for new activity compared to prior scans. All MRI scans will be read locally for safety and clinical purposes, and PIs will communicate any significant MS or non-MS findings to the primary neurologist (should they not be the primary neurologist). Any new lesion documented on the T_1 MRI scan will prompt delivery of a notice within 48 hours, to the PI, that the patient has achieved the endpoint of the study, with a description of relevant findings.

In the event of a suspected relapse, the patient will be instructed to contact their physician and the study coordinator at their local site within 48 hours of new symptoms and come in for an unscheduled visit and relapse evaluation within seven days of symptom onset. Use of corticosteroids will be at the discretion of the patient and the local PI or other physician. Use of systemic steroids to treat MS symptoms will be concluded to be a Protocol-defined relapse. As at scheduled visits, the determination of a relapse at an unscheduled visit will be made by the blinded EDSS examiner, who will perform the EDSS and only then receive information about recent clinical history.

D. Risks/Safety:

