Blinding of outcome measures is very important. As this is a pragmatic study in which the research component is added on to the basic clinical visit, the Treating Physician/PI will have obtained a relapse history as part of that routine visit, yet is not blinded to the patient's medication assignment. The definition of relapse includes performance of the EDSS, and the separate EDSS Examining Clinician will be blinded to medication assignment, as well as to the relapse history, when doing the EDSS. While it might be preferential to have a relapse assessor separate from both the PI and the EDSS rater, this is impractical due to costs, the requirement to have a third clinician available at the visit, and the extra time of the visit. Thus, we will ask the PI to do a relapse assessment based on symptoms, but only make this information available to the EDSS Examining Clinician AFTER the EDSS is completed. The EDSS Examining Clinician will make the final assessment as to whether a Protocol defined relapse has occurred. While MRI readers and Examining Clinicians will be blinded to the patient's medication assignment, patients will not be blinded to medication assignment. Thus interpretation of the secondary Aims and Hypotheses as they relate to PROs will be potentially confounded by patient bias.

It is possible a patient may have asymptomatic changes on a surveillance spine MRI scan, which is not part of the protocol or SOC. Most new spine lesions will have clinical symptoms and signs associated with them, however, limiting the significance of this issue.

This protocol, if taken as an independent study of participants who have been randomized and followed on treatment or off treatment for two years for an additional follow-up period will not have sufficient power to answer the question of non-inferiority during this extension period. If taken as a continuation of the original protocol, it then operates under the power considerations designed in the original protocol (NCT03073603). We acknowledge the insufficient power of this extension study to address non-inferiority, but still expect to obtain valuable information. Through this extension, we will be able to track rates of relapse or MRI scan changes and collect information on effects of withdrawal from therapy, disease progression, and quality of life of these older MS participants over a longer follow-up period.

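### The unblinded PI's relapse assessment reaches the examiner before the final relapse call, and nothing requires it to omit the PI's conclusion or clues to the arm

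*Combined protocol and SAP*

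**What the plan says.** Section II (Background) states without qualification that "observers of the main outcomes (relapses, MRI changes and the EDSS) will be blinded".

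Section III.E (Potential Scientific Problems) sets out how this is to work:

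- **PI.** "the Treating Physician/PI will have obtained a relapse history as part of that routine visit, yet is not blinded to the patient's medication assignment".
- **Examiner.** The separate EDSS examiner "will be blinded to medication assignment, as well as to the relapse history, when doing the EDSS".
- **Hand-over.** "we will ask the PI to do a relapse assessment based on symptoms, but only make this information available to the EDSS Examining Clinician AFTER" scoring is finished.
- **Decision.** "The EDSS Examining Clinician will make the final assessment as to whether a Protocol defined relapse has occurred".
- **Alternative considered.** "While it might be preferential to have a relapse assessor separate from both the PI and the EDSS rater, this is impractical", for reasons of cost, staffing and visit time.

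Section III.C (Study Design and Research Methods) applies the arrangement at T1, where every participant has "a formal, blinded relapse assessment by the Examining Physician (EDSS rater) in conjunction with the PI (see section E", a cross-reference back to III.E. For a suspected relapse between visits, III.C says that "the determination of a relapse at an unscheduled visit will be made by the blinded EDSS examiner", who first does the EDSS and then receives recent clinical history. Section III.D (Risks/Safety) describes that second step as a review of the presenting symptoms. III.D also leaves the label of pseudo-relapse to the treating physician.

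**The concern.** The timing rule protects the EDSS score. It does not protect the step after it. Besides the examination change, a Protocol defined relapse needs a new or worse symptom attributable to MS, lasting at least 48 hours, without fever, after at least 30 days of stability or improvement. Those elements come from history and judgement, and the person who supplies them knows the arm. Section III.E calls what is handed over a relapse assessment, and no section says that it must leave out the PI's conclusion or anything that hints at treatment.

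The exposed cases are those where the examination has worsened by the required amount and the call is still doubtful. The EDSS threshold is low, at 0.5 point, and the trial admits progressive MS. A slow decline in such a patient could reach 0.5 point without a relapse, and then timing and attribution settle the call. If these calls lean by arm, the comparison of event proportions leans with them. Section III.F expects few events. The only bias caveat in III.E concerns patient-reported outcomes, so a reader of Section II would take the relapse endpoint to be fully blinded.

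**Working it through.** **1. What is handed over, section by section**

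| Place | Given to the examiner after the EDSS |
|---|---|
| III.E | The PI's symptom-based relapse assessment |
| III.C, T1 visit | Assessment made jointly with the PI, by reference to III.E |
| III.C, unscheduled visit | Recent clinical history |
| III.D, unscheduled visit | Presenting symptoms |

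The first two rows include a judgement by an unblinded person. The last two can be read as facts only. III.C introduces its unscheduled-visit rule as the same as at scheduled visits, so a site cannot tell which description governs.

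**2. Where the PI's view can act**

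- *No qualifying examination change* (0.5 EDSS point, or 1.0 on a listed functional system). The event cannot be Protocol defined, whatever the PI thinks, unless systemic steroids were given for MS symptoms. It is at most a suspected relapse, used in secondary analyses.
- *Not seen within 7 days.* Not Protocol defined, with the same steroid exception.
- *Qualifying change, seen in time.* Symptom timing, fever, prior stability and attribution decide. This is the exposed group.
- *New or enlarging MRI lesion.* Read centrally by a blinded neuro-radiologist. Not exposed, and such a participant is an event whatever the relapse call.

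**3. The plan's own figure**

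Inputs from III.F (Sample Size): 50 per arm, 10 events on discontinue and 3 on continue. For *a* and *b* events with *m* = *a* + *b*, the one-sided Fisher p-value is the sum over *k* ≥ *a* of C(50,*k*) × C(50,*m*−*k*) / C(100,*m*).

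- 10 vs 3 (*m* = 13): p = 0.0357. The plan's 0.036 is reproduced.

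**4. One call changed in that example**

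- 9 vs 3 (one discontinue event lost): p = 0.0606
- 10 vs 4 (one continue event added): p = 0.0739
- 11 vs 3 (one discontinue event added): p = 0.0204

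The plan states no threshold for this test. Against a one-sided 0.05, either of the first two changes crosses it.

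**5. Illustration against the 0.08 margin**

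Assumptions: low counts that the documents do not give, 50 per arm, and a simple Wald interval in place of the Kaplan-Meier interval. Upper bound = (p₁ − p₂) + 1.96 × √[p₁(1−p₁)/50 + p₂(1−p₂)/50], discontinue minus continue.

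- 3 vs 3: 0 + 1.96 × √[2 × 0.06 × 0.94/50] = 0.093, above 0.08
- 2 vs 3: −0.02 + 1.96 × √[0.04 × 0.96/50 + 0.06 × 0.94/50] = 0.065, below 0.08

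At these counts one call changes the answer. At others it does not: 2 vs 2 gives 0.077 and 1 vs 2 gives 0.047, both below 0.08. The planned comparison with 0.08 also links these data to the original DISCOMS curves, so this shows scale only.

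All these counts are composite events. The share open to the PI's influence could be anything from none to all of them.

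**The case against.** The strongest reply is that the protocol has thought about this. It calls blinding very important, weighs a third assessor and says why there is none. It puts the EDSS first, keeps the examiner blind to medication and gives the examiner the last word. The relapse assessment in III.E may be no more than a symptom report, which would agree with the wording in III.C and III.D. The CRF is not among the documents, so nobody can say that it carries a verdict. Section III.E also concedes that the extension lacks power for non-inferiority, and III.F makes estimation the main goal, so the 0.08 margin should not be leaned on too hard.

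Much of this stands. In particular, three stronger readings are not supported:

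- **That knowledge of the arm can reach the primary endpoint at every relapse evaluation.** The examination requirement and the 7-day window close the route in many evaluations, and MRI events never pass through it.
- **That the examiner is told the arm.** The documents say the opposite. The gap is only that nothing keeps clues out of the hand-over.
- **That the bias can be put at some number of percentage points.** Suppose 3 to 8 evaluations per arm, 10–20% of calls tipped, and opposite directions in the two arms. The shift is then 2 × 3 × 0.1/50 = 1.2 points to 2 × 8 × 0.2/50 = 6.4 points. None of these inputs is in the documents, and the sum applies tipping to evaluations without an examination change, where it cannot act. If half had a qualifying change, also an assumption, the range would be 0.6 to 3.2 points. If none did, it would be zero.

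One part of the reply does not stand. The reasons in III.E explain why there is no third clinician. They do not explain why the examiner should receive an opinion rather than facts.

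**Conclusion.** The concern holds in a limited form. The EDSS finding is protected. The symptom, timing and attribution part of a relapse call is open to an unblinded view once the examination has changed, and the sections differ on what the examiner may be given. The general statement in Section II that relapse observers are blinded needs that qualification.

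The size cannot be estimated from the documents, and the direction is unknown. What can be said is that single calls carry weight at this sample size, as the move from 0.036 to 0.061 shows. That rests on the plan's illustrative counts, and on the changed call being a relapse in a participant with no new MRI lesion. This is a cheap improvement to the procedure. It does not show that the endpoint is invalid.

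Two other unblinded routes are separate from this one: the automatic counting of steroid-treated symptoms as relapses, and the treating physician's say over pseudo-relapse. The second bears on the fix, because attribution is the main judgement left once the EDSS has changed.

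**What to change.** 1. Record and lock the EDSS and functional system scores before anything is handed over.
2. Then give the examiner a structured facts-only record: symptom, onset date, duration, fever or infection, and stability over the prior 30 days. It should carry no PI conclusion and no mention of DMT, side effects or arm.
3. Put the PI's own opinion on a separate CRF page that the examiner does not see.
4. Use one description of the hand-over in III.C, III.D and III.E, for scheduled and unscheduled visits alike.
5. Reconcile III.D, where the treating physician determines pseudo-relapse, with III.E, where the examiner makes the final relapse call.

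The cost is a change to the CRF and a few sentences of protocol text. No third assessor is needed, so the practical objection in III.E does not arise. The examiner loses the PI's clinical impression. The change narrows the route without closing it, because the same unblinded PI still records the facts.

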COMIRB Protocol

COLORADO MULTIPLE INSTITUTIONAL REVIEW BOARD [name] [contact] [contact]

Protocol #:	20-2772
Project Title:	Discontinuation of Disease Modifying Therapies (DMTs) in Multiple Sclerosis (MS): Extension of the DISCOMS Study
Principal Investigator:	[name]
Version Date:	12Aug2021

I. Hypotheses and Specific Aims:

Main hypothesis: The DISCOntinuation of disease modifying therapies (DMTs) in Multiple Sclerosis (MS-DISCOMS) study is a maximum two-year, randomized controlled clinical trial (RCT) assessing whether relatively older (55+), stable (no relapse for 5+ years, no new magnetic resonance imaging abnormalities of the brain or spine for 3+ years) MS patients who discontinue their DMT have no greater recurrence of disease activity compared to those who continue use of their DMT. We propose an extension of this trial in a 100-person subset of those from the original study who remain in their original drug assignment group at the end of the primary DISCOMS trial in order to continue to assess the duration of follow-up to more fully answer the question of the duration of safe withdrawal if that is the case. To date, the DSMB has not stopped the study, and the final participants have not completed the trial as yet. Thus, we have no new information on the equipoise of the original hypothesis. The **Main Hypothesis of this extension trial** is that among those who have successfully discontinued their DMT as part of the DISCOMS trial (i.e. did not have a new MS relapse or brain MRI lesion) and remain off DMT after DISCOMS are at no greater risk of new or worsened MS disease activity compared to those who successfully continued their DMT as part of DISCOMS and remain on DMT, each assessed at least one year after termination of the primary DISCOMS study.

Specific Aims:

In MS patients who participated in the primary DISCOMS trial, successfully completed a minimum of 18 months of the two year primary DISCOMS study and remained in their original assignment group (i.e. either have discontinued or continued their DMT or another DMT), we will compare clinically significant and patient-relevant outcomes in those who have persistently discontinued vs persistently continued DMTs to determine if:

- 1. Risk of new relapses or brain MRI lesions is no worse in those persistently discontinuing
- 2. Risk of disability progression (by the Extended Disability Status Scale EDSS) is no worse in those persistently discontinuing

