- During the primary DISCOMS study, no evidence of recent new inflammatory disease activity (inactive by the Lublin criteria¹⁶). Pseudorelapses due to infection, fever, or other stressors as deemed by the local PI will NOT be excluded. Those who have already successfully completed the primary DISCOMS study without having a new relapse or MRI scan change, but who have a relapse or scan change AFTER ending participation in DISCOMS but before entering the extension ARE eligible and will be recruited, i.e. we do not wish to undercount new activity that occurs after exiting DISCOMS.
- Provides informed consent to continue in the extension trial.
- Willing to follow the protocol.

• Able to undergo a brain MRI without anesthesia, as part of routine care (i.e. paid for by their insurance). * Continuously will be defined as no less than 75% of all prescribed doses, with no time of greater than four weeks from last intended dose to have missed a dose (8 weeks for natalizumab, i.e. one missed dose).

Exclusion criteria:

- During original DISCOMS trial participant was randomized to the discontinue group, but then either restarted their DMT during the trial (study-defined 'treatment withdrawal), or wishes to restart their DMT after completing original DISCOMS study. Conversely, also excluded are those who completed the primary trial in the continue group and then discontinued, or wishes to discontinue, after completion of the primary study.
- Any MS relapse or new MRI scan lesion (3 mm or larger) during the primary DISCOMS trial, with relapse determined by the blinded examiner and MRI lesion determined by the blinded MRI reader.
- Significant (as defined by the PI) intolerance of presently-used DMT, if taking a DMT
- The following must **not** have occurred during the original DISCO MS study or since completing the study:
 - Use of any non-FDA-approved DMT
 - More than two courses of acute, systemic (IV or oral). Course is defined as three or more days continuously, and not to exceed 14 days. No use of chronic, systemic steroids, defined as 15 or more days. Any use of steroids to treat MS relapse, possible relapse, or pseudo-relapse is excluded. Inhaled or topical steroids for non-MS are not exclusionary.
 - Use of alemtuzumab, mitoxantrone, cyclophosphamide, methotrexate, cyclosporine, rituximab, or cladribine.
 - \circ $\,$ Use of any experimental agent used as a DMT for MS $\,$
 - Cancers other than basal cell skin cancers

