a. Aim #1: Proposed Data Analysis: We will perform an extension of the primary DISCOMS study, that being the time to failure defined as a protocol-defined disease event with each treatment group extending the understanding of the durability of the assigned treatment arm beyond the original DISCOMS follow-up period. A countable event will be a new protocol-defined relapse, and/or a new brain MRI lesion. We will estimate the long-term differences between the two treatment arms. Further by linking the time to event within the 100 participants with the original DISCOMS event free survival estimates, we can further evaluate the null hypothesis of inferiority with the proportion of disease events for the discontinue group being 0.08 proportion worse (our original noninferiority margin) at later time points of follow-up than the proportion for the continue group under the alternative that the two rates are equal. Because of the expected small numbers of events, we will use Kaplan-Meier estimates of the differences to obtain a confidence interval for comparing the proportions with individuals counted at their respective event times or censored based on their last known status. If the upper bound of the 95% confidence interval for the difference between the groups is less than 0.08, then we can reject inferiority and rule out discontinuation increasing the disease event proportion by 0.08 or greater. Our primary goal here is to estimate these differences given the relatively small sample size included, but we will calculate these values using the data obtained. In the unlikely event the proportions are relatively large, we will also calculate estimates and confidence intervals for relative risks. Larger numbers of events would permit the fitting of more complex models, but to date we know that the majority have not failed although their assignments are not known to us.

b. Aim #2: Proposed Data Analysis: We will calculate estimates and confidence intervals, using exact methods as necessary, for the proportion of disease events in both the discontinue and continue groups after this extension

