study. Aim #2 will be mostly descriptive and assesses progression of disability as noted on the EDSS, and this will be defined as an increase of at least one point, confirmed at 6 months, for those with a baseline EDSS \leq 5.5, or a change of at least 0.5 for those with EDSS of 6.0 or greater at baseline. The estimates of the population from the origin of the study will be model based since participants in the extension study must by criteria have not had progression over the initial period of follow-up. Nevertheless, we will have the proportion at the end of the formal DISCOMS study and can apply the successive failure rates using conditional probability to obtain an overall estimate of the progression rate after 2 or 3 years and further can compare the post DISCOMS experience between the two arms given the participants were free of events at entry into the Extension study. Outcomes assessed will include % of patients with progression in each group as compared to the final EDSS in DISCOMS, and mean change in EDSS in each group overall (via the extension period. The latter analyses will help identify if the rate is increasing over time or if the rate is relatively stable over time.

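### The 0.08 non-inferiority rule is applied to event-free survival since DISCOMS randomization, whereas the extension's Main Hypothesis concerns risk after DISCOMS in people event-free there

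*Combined protocol and SAP*

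**What the plan says.** Section I states the Main Hypothesis of the extension. People who came through DISCOMS without an event and stayed off DMT "are at no greater risk of new or worsened MS disease activity compared to those who successfully continued their DMT as part of DISCOMS". The comparison group must likewise have kept taking a DMT, with the two groups "each assessed at least one year after termination of the primary DISCOMS study". The exclusion criteria in section III.B build the cohort for that question by removing anyone with "Any MS relapse or new MRI scan lesion (3 mm or larger) during the primary DISCOMS trial".

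Section III.F, Aim #1 states: "by linking the time to event within the 100 participants with the original DISCOMS event free survival estimates, we can further evaluate the null hypothesis". That null is inferiority, namely that the discontinue group is "0.08 proportion worse (our original noninferiority margin) at later time points of follow-up". Inferiority is rejected if the upper 95% limit is below 0.08. Section III.C describes the completed Kaplan-Meier curve as serving the hypothesis of the original trial.

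A comparison restricted to people event-free at entry is spelled out only under Aim #2, which assesses EDSS progression and is called mostly descriptive. There the plan "can compare the post DISCOMS experience between the two arms given the participants were free of events at entry into the Extension study". No margin or rule goes with it.

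**The concern.** The hypothesis is conditional on being event-free at DISCOMS exit. The quantity tested is cumulative from randomization, so it also carries the DISCOMS failures, none of whom can be in the extension. Two trials with identical post-DISCOMS risks can therefore get opposite verdicts from the rule because their DISCOMS phases differed.

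A fail could largely repeat a DISCOMS disadvantage when persistent discontinuers have no excess risk afterwards. A pass could reflect a DISCOMS advantage that hides a later excess. In neither case has the stated hypothesis been judged, and the plan does not say which Aim #1 estimate answers it.

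**Working it through.** **The plan's own figure.** The Sample Size paragraph gives a one-sided Fisher p-value of 0.036 for 10/50 v 3/50. Recomputed: 0.0357 (two-sided 0.071), so it reproduces. It uses extension data only and illustrates detecting harm; it is not the rule at issue.

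**Inputs from the documents.**
- DISCOMS: 260 enrolled, 1:1 (section II), taken as 260/2 = 130 per arm.
- Extension: about 50 per arm (Sample Size), or about 59 discontinue / 41 continue (section III.C).
- Margin 0.08, upper 95% limit (Aim #1). Sidedness is not stated; a two-sided interval is assumed, z = 1.96.

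**Assumed.** DISCOMS event risk F and post-DISCOMS risk g in each arm, with complete follow-up. The documents give no DISCOMS rates, so F is varied.

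**Formulas.** Let S = 1 − F and q = 1 − g.
- Linked difference (discontinue minus continue): D = S_c·q_c − S_d·q_d.
- Variance per arm: q²·S·F/130 + S²·q·(1 − q)/50.
- Pass if D + 1.96·SE < 0.08.

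If g is the same in both arms, D = q·(F_d − F_c): the linked difference is then just the DISCOMS difference, slightly shrunk.

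**Two single data sets.**
- DISCOMS 16/130 discontinue v 6/130 continue, then 0/50 v 0/50. D = 0.9538 − 0.8769 = 0.077. SE = √(0.8769×0.1231/130 + 0.9538×0.0462/130) = 0.0342. Upper limit 0.144: fail, with no post-DISCOMS event in either arm.
- DISCOMS 2/130 v 20/130, then 5/50 v 1/50. D = 0.8462×0.98 − 0.9846×0.90 = −0.057. SE = 0.0555. Upper limit 0.052: pass, although the post-DISCOMS difference is 0.10 − 0.02 = +0.08 (Newcombe upper limit 0.195).

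**Probability that the linked rule passes** (200,000 simulations per row, 50 per arm; risks are discontinue / continue):

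| Post-DISCOMS risk | DISCOMS risk | True D | P(pass) |
|---|---|---|---|
| 4% / 4% | 5% / 12% | −0.067 | 0.85 |
| 4% / 4% | 5% / 5% | 0 | 0.45 |
| 4% / 4% | 10% / 5% | 0.048 | 0.11 |
| 4% / 4% | 12% / 5% | 0.067 | 0.05 |
| 12% / 4% | 5% / 5% | 0.076 | 0.04 |
| 12% / 4% | 5% / 15% | −0.020 | 0.40 |
| 12% / 4% | 2% / 12% | −0.018 | 0.41 |
| 12% / 4% | 2% / 15% | −0.046 | 0.57 |

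A 59/41 split changes these by less than 0.02. The 0.45 at 5%/5% reflects ordinary imprecision; the movement away from it, with post-DISCOMS risk unchanged, is the effect of the DISCOMS phase.

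**Extension alone.** If the 0.08 rule were moved to the post-DISCOMS difference, with 50 per arm and a true risk of 4% in both, power would be 0.34 (Newcombe) or 0.59 (Wald). With Newcombe limits, 0/50 v 0/50 passes (0.071) and 1/50 v 1/50 does not (0.087). This fits the low power conceded in section III.E.

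**The case against.** The plan has a reasonable defence.

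- **Estimation comes first.** Aim #1 calls estimation its primary goal and, before it mentions linking, promises long-term differences between the arms. Section III.E separates the reading as a stand-alone study from the reading as a continuation of DISCOMS and concedes low power for the former. This softens the consequence. But the promised estimate has no time origin or population, and section III.E does not say which reading answers the Main Hypothesis.
- **The Aim #2 text overlaps.** It speaks of disease events, which is Aim #1's term, and describes the conditional comparison. That shows the authors saw the right quantity; it still sits under a different aim and endpoint.
- **The linked rule is not the only inferential statement.** The Fisher illustration uses extension data alone. It could indicate harm, but a non-significant result there could not show no greater risk.

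A reader might also infer that a large late excess would readily slip through whenever the linked difference stays inside 0.08. The rule does not support that, because it uses the upper limit. Take DISCOMS risks of 6% discontinue / 8% continue, then 12% / 2%: D = 0.92×0.98 − 0.94×0.88 = 0.074, but the upper limit is 0.183. Take 10% / 10%, then 10% / 2%: D = 0.072, upper limit 0.179. Each passes only about 5% of the time.

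**Conclusion.** The mismatch is real: the one rule that can support no greater risk does not judge the extension's stated hypothesis. With post-DISCOMS risk equal at 4%, its pass probability runs from 0.85 to 0.05 as the assumed DISCOMS risks change.

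The two directions are not equally likely. A DISCOMS disadvantage of 5 points (10% v 5%) is enough to cut the pass probability from 0.45 to 0.11. A pass despite a post-DISCOMS excess of 0.08 has probability 0.04 when the DISCOMS arms were equal at 5%, and reaches 0.40 or more in the cases tried only when discontinuers did at least 10 points better in DISCOMS.

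Two stronger readings should be avoided. The rule is not unrelated to the hypothesis: extension risks enter the linked difference directly, so it is influenced by the DISCOMS phase rather than irrelevant. Nor do the documents say that passing it would establish the extension hypothesis; they leave the link unstated. Failing to reject inferiority is not itself a finding of harm.

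The probabilities rest on assumed DISCOMS and extension rates, 130 and 50 per arm, complete follow-up and a two-sided 95% interval. The mismatch in the text does not depend on them.

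**What to change.** In section III.F, Aim #1:

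- Name as the analysis of the Main Hypothesis the between-arm difference in event risk from DISCOMS exit among extension participants, with a 95% interval. Report it as an estimate, consistent with section III.E.
- Report it through T1, with a method that allows for differing follow-up and for MRI lesions known only to have arisen between scans. A Kaplan-Meier reading at exactly 12 months is not enough on its own: Table 2 schedules a single MRI, and section III.C allows T1 up to 30 months after DISCOMS ends.
- Keep the linked curve and its 0.08 rule, labelled as a statement about cumulative risk since randomization, that is, the original DISCOMS hypothesis. State that passing or failing it does not by itself decide the extension hypothesis.

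The cost is plan wording and one further analysis of data already being collected, including the choice of an interval-censoring method. No visits or participants are added. The downside is that the Main Hypothesis gets a wide-interval estimate rather than a possible non-inferiority claim.
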